#### 9.3.2.3.5 [REDACTED]

[REDACTED]

[REDACTED] (37)

[REDACTED]

[REDACTED]

[REDACTED]

[REDACTED]

[REDACTED]

### 9.3.2.3.6 Assessment of Causality

The Investigator will assess the *causal relationship* between each unsolicited systemic AE and vaccination as either not related or related, based on the following definitionsa:

- 0: Not related – The AE is clearly/most probably caused by other etiologies such as subject’s underlying condition, therapeutic intervention, or concomitant therapy; or the delay between vaccination and the onset of the AE is incompatible with a causal relationship; or the AE started before the vaccination (screening phase, if applicable)
- 1: Related – There is a “reasonable possibility” that the AE was caused by the vaccination, meaning that there is evidence or arguments to suggest a causal relationship

Note: By convention, all injection site AEs (solicited and unsolicited) and all solicited systemic reactions are considered to be related to vaccination and referred to as reactions, and therefore do not require the Investigator’s opinion on relatedness.

AEs likely to be related to the product, whether serious or not, that persist at the end of the trial will be followed up by the Investigator until their complete disappearance or the stabilization of the subject’s condition. The Investigator will inform the Sponsor of the date of final disappearance of the event.

### 9.3.3 Efficacy

No clinical efficacy data will be obtained in the trial.

## 10 Reporting of Serious Adverse Events

In order to comply with current regulations on SAE reporting to health authorities, the Investigator must document all SAEs regardless of causal relationship, and notify the Sponsor and the Clinical Research Associate (CRA) within the notification timelines stated in the following sections. The Investigator will give access and provide the Sponsor and the CRA with all necessary information to allow the Sponsor to conduct a detailed analysis of the safety of the investigational product(s). It is the responsibility of the Investigator to request all necessary documentation (e.g., medical records, discharge summary, autopsy) in order to provide comprehensive safety information. All relevant information must then be transcribed into the electronic Serious Adverse Event (eSAE) Form.

### 10.1 Initial Reporting by the Investigator

SAEs occurring during a subject’s participation in the trial or experiment must be reported within 24 hours to the Sponsor’s GPV Department and to the CRA. Every SAE must be reported, even if the Investigator considers that it is not related to the vaccine. The SAE form must be signed by a

---

a ICH Guidelines, Clinical Safety Data Management E2A

licensed physician (M.D. or D.O.) for whom the task is listed on the Study Task Delegation and Signature List after each update to the Form.

The Investigator must complete the “eSAE Form” in the EDC application. After validation, an e-mail alert will automatically be sent to the GPV mailbox, the CRA and the CTL. This message will include the country, the study code, the subject number, whether the report is initial or a follow-up, the diagnosis and/or symptoms, the seriousness criteria, the relationship, if related, and the outcome, if fatal.

If the EDC system is unavailable, the site must notify the Sponsor using the paper version of the SAE Reporting Form, as follows:

The Investigator must complete the SAE Reporting Form, check off the “Initial Reporting Form” box, and send it to the Sponsor by one of the following means (preferably by fax or e-mail):

- By fax, to the following number: [REDACTED]
- In PDF format to the following e-mail address, using a method of transmission that includes password protection: [REDACTED] (see the Operating Guidelines for directions on how to send a password-protected email)
- By express mail, to the following address: Sanofi Pasteur Inc.  
Reception and Triage – Case Management  
Global Pharmacovigilance  
[name]  
[name]  
[name]

When the system becomes available, the Investigator must transcribe the information from the paper version of the eSAE Form into the EDC system.

If there is need for urgent consultation, the Investigator is to contact the RMO. If the RMO cannot be reached, the Investigator may contact the Call Center as described in [Section 5.3](#).

## 10.2 Follow-up Reporting by the Investigator

The eSAE Form completed initially must be updated within 24 hours after the Investigator has become aware of any new relevant information concerning the SAE (e.g., outcome, precise description of medical history, results of the investigation). After validation, an e-mail alert will be sent automatically to the GPV Department and to the CRA. All relevant information must be included directly in the eSAE form. Copies of documents (e.g., medical records, discharge summary, autopsy) may be requested by the GPV Department.

The anonymity of the subject must always be respected when forwarding this information.

### 10.3 Reporting of SAEs Occurring After a Subject Has Completed the Study

Any SAE that occurs after a subject has completed the study but that is likely to be related to the product or to the experiment must also be reported as soon as possible. In such a case, the reporting procedure to be followed is identical to that described in [Section 10.1](#).

### 10.4 Assessment of Causality

The causal relationship between the SAE and the product will first be evaluated by the Investigator, using the following definitions:

**0 - Not related:** The AE is clearly/most probably caused by other etiologies such as an underlying condition, therapeutic intervention, or concomitant therapy; or the delay between vaccination and the onset of the SAE is incompatible with a causal relationship; or the SAE started before the vaccination (screening phase, if applicable).

**1 - Related:** There is a “reasonable possibility” that the SAE was caused by the vaccination, meaning that there is evidence or arguments to suggest a causal relationship.

*(ICH Guidelines, Clinical Safety Data Management E2A)*

Following this, the Sponsor’s Product Safety Officer (PSO) will also assess the causal relationship to the product, based on the available information and current medical knowledge.

The decision to modify or discontinue the trial may be made after mutual agreement between the Sponsor and the Investigators.

### 10.5 Reporting SAEs to Health Authorities and IECs/IRBs

The Sponsor will inform the relevant health authorities of any reportable SAEs according to the local regulatory requirements. Reporting to the health authorities will be according to the Sponsor’s standard operating procedures.

The Sponsor’s RMO [REDACTED], [REDACTED], [REDACTED] will notify the Investigators in writing of the occurrence of any reportable SAEs. The Investigators and/or Sponsor will be responsible for informing the IECs or IRBs that reviewed the trial protocol, according to local regulations.

## 11 Data Collection and Management

### 11.1 Data Collection and CRF Completion

Individual safety diary cards, specifically designed for this trial by the Sponsor and provided to the study sites, will be given to study participants for the recording of daily safety information as described in [Section 9.3.2.3](#). These diary cards will include prelisted terms and intensity scales (see [Table 9.1](#) and [Table 9.2](#)) as well as areas for free text to capture additional safety information or other relevant details. Parents/Legally acceptable representatives will also be provided with

rulers for measuring the size of injection site reactions, and with standard digital thermometers for measuring daily temperatures. To ensure consistency of reporting, the study sites will instruct parents/legally acceptable representatives on how to correctly use these tools.

Relevant information will be transcribed into the CRF. Any SAEs, [REDACTED], captured during this 30-day follow-up period will be reported and followed-up as per the normal process for reporting SAEs.

At specified intervals, the Investigator or an authorized designee will interview the parents/legally acceptable representatives to collect the information recorded in the DC, and will attempt to clarify anything that is incomplete or unclear. All clinical trial information gathered by the study site will be reported electronically by the Investigator or authorized designee using a web-based CRF. (Any information that was not documented in the DC will first be captured in the source document and then reported electronically.) The CRF has been designed specifically for this trial under the responsibility of the Sponsor, using a validated Electronic Records/Electronic Signature-compliant platform (21 CFR Part 11).

To ensure the correct and consistent completion of the CRFs, the Sponsor or authorized representative will provide all necessary tools, instructions, and training to all site staff involved in data entry prior to study start. Additional instructional documents such as training manuals and completion guidelines will be provided to assist with data entry during the course of the trial.

Upon completion of training, each user requiring access to the EDC system will be issued a unique username and password. In the event of a change in trial personnel, each newly assigned individual will receive a unique username and password; the username and password of a previous user may not be reissued. If any trial personnel leave the study, the Investigator is responsible for informing the Sponsor immediately so that their access is deactivated. An audit trail will be initiated in the EDC system at the time of the first data entry in order to track all modifications and to ensure database integrity.

The Investigator is responsible for the timeliness, completeness, and accuracy of the information in the CRFs; must provide explanations for all missing information; and must sign the CRF using an e-signature.

## 11.2 Data Management

### *Management of Clinical Data*

Data generated during the trial will be managed following 2 different processes:

- Clinical data, defined as all data reported in the CRF, and laboratory data will be handled by the Sponsor's Clinical Data Management (CDM) platform or authorized representative.
- Data pertaining to SAEs, which are reported by the Investigator on the eSAE Forms or SAE Reporting Forms, will be handled by the Sponsor's GPV Department.

During the trial, clinical data reported in the CRFs will be integrated into the clinical database under the responsibility of the Sanofi Pasteur CDM platform. Data monitoring at the sites and quality control in the form of computerized logic and/or consistency checks will be systematically

applied in order to detect errors or omissions. In addition, data reviews may be performed several times by the Sponsor's staff in the course of the trial. Any questions pertaining to the reported clinical data will be submitted to the investigator for resolution using the EDC system. Each step of this process will be monitored through the implementation of individual passwords to maintain appropriate database access and to ensure database integrity.

The validation of the immunogenicity data will be performed at the laboratory level following the laboratory's procedures. Information from the laboratory will be checked for consistency before integration into the clinical database.

After integration of all corrections in the complete set of data, and after the SAE information available from CDM and the GPV Department has been reconciled, the database will be released for statistical analysis.

### **SAE ( ) Data Management**

During the trial, data pertaining to SAEs reported on eSAE Forms will be integrated into the Sponsor's centralized GPV database.

Upon receipt of an eSAE Form, the data will be entered into the GPV database after a duplicate check. Each SAE case will be assigned a case identification number. Each case will be entered in the GPV database and assessed by the case management platform or its delegate before being reported to the relevant authorities as necessary. Assessment of related cases will be done in collaboration with the PSO and the RMO. Follow-up information concerning a completed case will be entered into the GPV database, and a new version of the case will be created.

The information pertaining to SAEs in the GPV database will be reconciled with that in the clinical database.

## **11.3 Data Review**

A blind review of the data is anticipated through the data review process led by Data Management before database lock. The safety of the investigational product will be continuously monitored by the Sponsor. Periodic safety data review will be performed by the Sponsor's SMT. For all periodic safety reviews, blinded safety data will be provided to the Sponsor's SMT.

## **12 Statistical Methods and Determination of Sample Size**

### **12.1 Statistical Methods**

Clinical data will be analyzed under the responsibility of the Biostatistics Platform of the Sponsor. A statistical analysis plan (SAP) will be written and peer reviewed before any analyses. In accordance with the protocol, the SAP will describe all analyses to be performed under the responsibility of the Sponsor and all the conventions to be taken.

## 12.1.1 Hypotheses and Statistical Methods for Primary Objectives

Two co-primary objectives will be evaluated.

### 12.1.1.1 Primary Objective 1

***Non-inferiority testing after 1 dose of MenACYW conjugate vaccine or Nimenrix® in toddlers who either are meningococcal vaccine naïve or have received monovalent MenC vaccination during infancy***

The percentages of subjects who achieve an hSBA titer  $\geq 1:8$  for meningococcal serogroups A, C, Y, and W in toddlers who received MenACYW conjugate vaccine (Group 1 and Group 3) are non-inferior to the corresponding percentages in toddlers who received Nimenrix® (Group 2 and Group 4) 30 days post administration.

Null hypothesis ( $H_0$ ):  $p_{(\text{Men})} - p_{(\text{Nim})} \leq -10\%$

Alternative hypothesis ( $H_1$ ):  $p_{(\text{Men})} - p_{(\text{Nim})} > -10\%$

where  $p_{(\text{Men})}$  and  $p_{(\text{Nim})}$  are the percentages of subjects who achieve an hSBA titer  $\geq 1:8$  in the MenACYW vaccine group and the Nimenrix® group, respectively. Each of the serogroups A, C, Y, and W will be tested separately. If the lower limit of the 2-sided 95% confidence interval (CI) of the difference between the 2 percentages is  $> -10\%$ , the inferiority assumption will be rejected.

For the 4 non-inferiority hypotheses using the response rates (percentages of subjects who achieve an hSBA titer  $\geq 1:8$ ), the 95% CI will be stratified on the priming status (meningococcal vaccine naïve or primed monovalent MenC vaccination during infancy) and calculated using the Wald method (normal approximation). Weighted average of the difference over strata will be calculated using the Minimal Risk weights with the null variance method (43).

The overall non-inferiority of this objective will be demonstrated if all 4 individual null hypotheses are rejected.

### 12.1.1.2 Primary Objective 2

***Non-inferiority testing after 1 dose of MenACYW conjugate vaccine or Nimenrix® in meningococcal vaccine naïve toddlers***

Thirty days after the administration of MenACYW conjugate vaccine or Nimenrix®, the percentages of subjects who achieve an hSBA titer  $\geq 1:8$  for meningococcal serogroups A, C, Y, and W in Group 1 are non-inferior to the corresponding percentages in Group 2.

Null hypothesis ( $H_0$ ):  $p_{(G1)} - p_{(G2)} \leq -10\%$

Alternative hypothesis ( $H_1$ ):  $p_{(G1)} - p_{(G2)} > -10\%$

where  $p_{(G1)}$  and  $p_{(G2)}$  are the percentages of subjects who achieve an hSBA titer  $\geq 1:8$  in Group 1 and Group 2, respectively. Each of the serogroups A, C, Y, and W will be tested separately. If the lower limit of the 2-sided 95% CI of the difference between the 2 percentages is  $> -10\%$ , the inferiority assumption will be rejected.

For the 4 non-inferiority hypotheses using the response rates (percentages of subjects who achieve an hSBA titer  $\geq 1:8$ ), the CI of the difference in proportions will be computed using the Wilson

Score method without continuity correction (44). The overall non-inferiority of this objective will be demonstrated if all 4 individual null hypotheses are rejected.

To conclude, non-inferiority in toddlers who either are meningococcal vaccine-naïve or have received monovalent MenC vaccination during infancy and non-inferiority in meningococcal vaccine-naïve subjects have to be demonstrated.

### **12.1.2 Hypotheses and Statistical Methods for Secondary Objectives**

No hypotheses will be tested. Descriptive statistics will be presented.

#### **12.1.2.1 Secondary Objective 1**

Thirty days after the administration of MenACYW conjugate vaccine or Nimenrix® in toddlers who either are meningococcal vaccine naïve or have received monovalent MenC vaccination during infancy, the hSBA geometric mean titer ratio (GMTR) between MenACYW conjugate vaccine or Nimenrix® will be calculated, and 95% CI will be provided. The 95% CI of the ratio of post-vaccination GMTs will be stratified on the priming vaccination status (meningococcal vaccine naïve or primed monovalent MenC vaccination) and calculated using an analysis of variance (ANOVA) model of log10-transformed titers.

#### **12.1.2.2 Secondary Objective 2**

Thirty days after the administration of MenACYW conjugate vaccine or Nimenrix® in meningococcal vaccine naïve toddlers, the hSBA GMTR between MenACYW conjugate vaccine or Nimenrix® will be calculated, and 95% CI will be provided.

#### **12.1.2.3 Secondary Objective 3**

Thirty days after the administration of MenACYW conjugate vaccine or Nimenrix® in toddlers who received monovalent MenC vaccination during infancy, the hSBA GMTR between MenACYW conjugate vaccine or Nimenrix® will be calculated, and 95% CI will be provided

### **12.1.3 Statistical Methods for Observational Objectives**

#### ***Immunogenicity***

Descriptive statistics will be provided for the antibody titers against meningococcal serogroups contained in MenACYW conjugate vaccine and Nimenrix®. In general, categorical variables will be summarized and presented by frequency counts, percentages, and CIs. The 95% CIs of point estimates will be calculated using the normal approximation for quantitative data and the exact binomial distribution (Clopper-Pearson method) for percentages (45). For GMTs, 95% CIs of point estimates will be calculated using normal approximation assuming they are log-normally distributed.

Reverse cumulative distribution curve (RCDC) figures will be provided for the antibody titers against meningococcal serogroups contained in MenACYW conjugate vaccine and Nimenrix® treatment groups.

In summary, descriptive analyses on A, C, Y, and W serogroups will include but not be limited to:

- hSBA GMT and 95% CI at D0 and D30
- hSBA titer distribution and RCDC
- Percentage of subjects with hSBA titer  $\geq 1:4$  and  $\geq 1:8$  and 95% CI at D0 and D30
- Percentage of subjects with hSBA titer  $\geq 4$ -fold rise from pre-vaccination to post-vaccination, and 95% CI
- hSBA vaccine seroresponsea rate and 95% CI
- rSBAb GMT and 95% CI at D0 and D30
- rSBAb titer distribution and RCDC
- Percentage of subjects with rSBAb titer  $\geq 4$ -fold rise from pre-vaccination to post-vaccination, and 95% CI
- rSBAb vaccine seroresponsec rate and 95% CI
- Percentage of subjects with rSBAb titers  $\geq 1:8$  and  $\geq 1:128$  and 95% CI at D0 and D30

### ***Safety***

For this trial, the safety data will be assessed by applying descriptive statistical methods, supplemented by the calculation of CIs to aid interpretation. The exact binomial distribution (Clopper-Pearson method) for proportions will be used in the calculation of the 95% CIs of events.

The frequency and percentage of subjects who had solicited injection site reactions and solicited systemic reactions and their 95% CIs will be provided. These events will be tabulated by the type of reactions and intensity for each study group. These events will also be summarized by other categories specified in the endpoints (e.g. time of onset, number of days of occurrence, actions taken).

Unsolicited AEs will be collected, coded, and summarized by MedDRA system organ class and preferred term. For each unsolicited AE, the number of subjects with at least 1 instance of that event will be reported. Unsolicited AEs will also be tabulated by intensity and relatedness of study vaccine and by other categories specified by the endpoints.

---

a hSBA vaccine seroresponse is defined as:

- For a subject with a pre-vaccination titer  $< 1:8$ , the post-vaccination titer must be  $\geq 1:16$ .
- For a subject with a pre-vaccination titer  $\geq 1:8$ , the post-vaccination titer must be at least 4-fold greater than the pre-vaccination titer.

b In a subset of subjects per group: 100 subjects each in Group 1 and Group 2; 50 subjects in each subgroup (MenC-TT or MenC-CRM primed subjects) in Group 3; 25 subjects in each subgroup (MenC-TT or MenC-CRM primed subjects) in Group 4

c rSBA vaccine seroresponse is defined as a post-vaccination titer  $\geq 1:32$  for subjects with pre-vaccination rSBA titer  $< 1:8$ , or a post-vaccination titer  $\geq 4$  times the pre-vaccination titer for subjects with pre-vaccination rSBA titer  $\geq 1:8$ .

Immediate reactions, SAEs, [REDACTED]s, and any event that leads to subject withdrawal from the study will be tabulated separately.

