## 5 Investigational Plan

### 5.1 Description of the Overall Trial Design and Plan

#### 5.1.1 Trial Design

This will be a Phase III, modified double-blind, randomized, parallel-group, active-controlled, multi-center trial to compare the immunogenicity and describe the safety of a single dose of MenACYW conjugate vaccine to a single dose of a licensed quadrivalent meningococcal polysaccharide groups A, C, W-135, and Y conjugate vaccine, Nimenrix®, in toddlers (12 to 23 months of age) in the EU who are either meningococcal vaccine naïve or received monovalent MenC vaccination during infancy.

Approximately 918 healthy toddlers aged 12 to 23 months will be enrolled and randomized as follows depending on the meningococcal background:

**Meningococcal Vaccine-Naïve Subjects:** 612 subjects will be randomized in a 1:1 ratio to the following 2 groups:

- Group 1: MenACYW conjugate vaccine (n=306)
- Group 2: Nimenrix® (n=306)

**MenC-Primed Subjects:** 306 subjects will be randomized in a 2:1 ratio to the following 2 groups:

- Group 3: MenACYW conjugate vaccine (n=204)
- Group 4: Nimenrix® (n=102)

Enrollment of MenC-primed subjects will be stratified by the type of primed vaccine, MenC-TT (NeisVac-C®) or MenC-CRM (Menjugate®, Meningitec®), considering that at least 25% and a maximum of 50% of subjects will have been primed with MenC-CRM as described in [Table 5.1](#).

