## 9.3 Observational Endpoints and Assessment Methods

### 9.3.1 Immunogenicity

#### 9.3.1.1 Immunogenicity Endpoints

The observational endpoints for immunogenicity are:

- Antibody titers  $\geq 1:8$  and  $\geq 1:128$  against meningococcal serogroups A, C, Y, and W measured by rSBA assessed before and at 30 days (+14 days) after vaccination with MenACYW conjugate vaccine or Nimenrix®
- Antibody titers against meningococcal serogroups A, C, Y, and W measured by hSBA and rSBA before and 30 days (+14 days) after vaccination with MenACYW conjugate vaccine or Nimenrix®.

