Unsolicited AEs will be collected, coded, and summarized by MedDRA system organ class and preferred term. For each unsolicited AE, the number of subjects with at least 1 instance of that event will be reported. Unsolicited AEs will also be tabulated by intensity and relatedness of study vaccine and by other categories specified by the endpoints.

Immediate reactions, SAEs, [REDACTED], and any event that leads to subject withdrawal from the study will be tabulated separately.

Safety tables will be described for subjects who are either meningococcal vaccine naïve or had received monovalent MenC vaccination during infancy (i.e. Group 1 & 3 and Group 2 & 4) and for subjects in all study groups (i.e. based on MenC priming vaccination background).

¹ hSBA vaccine seroresponse is defined as:

- For a subject with a pre-vaccination titer $<$ 1:8, the post-vaccination titer must be \geq 1:16.
 - For a subject with a pre-vaccination titer \geq 1:8, the post-vaccination titer must be at least 4-fold greater than the pre-vaccination titer.
- ² In a subset of subjects per group: 100 subjects each in Group 1 and Group 2; 50 subjects in each subgroup (MenC-TT or MenC-CRM primed subjects) in Group 3; 25 subjects in each subgroup (MenC-TT or MenC-CRM primed subjects) in Group 4
- ³ rSBA vaccine seroresponse is defined as a post-vaccination titer \geq 1:32 for subjects with pre-vaccination rSBA titer $<$ 1:8, or a post-vaccination titer \geq 4 times the pre-vaccination titer for subjects with pre-vaccination rSBA titer \geq 1:8.

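### Whole-vaccine rSBA summaries, and Group 3 or 4 rSBA summaries unless MenC-CRM enrolment reaches 50%, would reflect the subset quotas rather than the trial groups

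*Protocol*

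**What the plan says.** Protocol 5.1.1 sets the enrolment mix. Among vaccine-naive toddlers "612 subjects will be randomized in a 1:1 ratio", and among MenC-primed toddlers "306 subjects will be randomized in a 2:1 ratio". For the primed children, "at least 25% and a maximum of 50% of subjects will have been primed with MenC-CRM". Table 5.1 turns that range into 52 to 102 MenC-CRM children of 204 in Group 3, and 26 to 51 of 102 in Group 4.

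The rSBA subset does not follow that mix. Footnote b of Protocol 12.1.3 fixes "100 subjects each in Group 1 and Group 2; 50 subjects in each subgroup (MenC-TT or MenC-CRM primed subjects) in Group 3" and "25 subjects in each subgroup (MenC-TT or MenC-CRM primed subjects) in Group 4". SAP 5.1.3.2, footnote 2, repeats the quotas, for example "50 subjects in each subgroup (MenC-TT or MenC-CRM primed subjects) in Group 3".

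The planned rSBA outputs in both documents are GMTs, percentages above cut-offs, four-fold rises, seroresponse rates and RCDCs. The intervals are Clopper-Pearson for percentages and, for GMTs, a t interval on log10 titres (SAP section 5, text after Table 5.1). No weight or stratified estimate for rSBA appears in these sections, which are not redacted.

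Several places point to combined summaries. Protocol 2.3 has separate objectives to describe responses after each vaccine in toddlers generally. The endpoint in Protocol 9.3.1.1 covers titres "measured by hSBA and rSBA before and 30 days (+14 days) after vaccination with MenACYW conjugate vaccine" or Nimenrix. The RCDC "figures will be provided for the antibody titers against meningococcal serogroups contained in MenACYW conjugate vaccine and Nimenrix" treatment groups. Protocol 2.3 also asks for separate descriptions in MenC-TT-primed and MenC-CRM-primed children.

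**The concern.** Fixed quotas set against a different enrolment mix make the subset a disproportionate stratified sample. An unweighted summary across strata then estimates the average for the quota mix, not for the group named in the column. The two differ whenever responses differ by priming history.

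The plan allows for such differences elsewhere. It stratifies the pooled hSBA comparison and the pooled GMT ratio on priming status (Protocol 12.1.1.1 and 12.1.2.1), and Protocol 5.1.2 plans descriptive analyses to allow for the MenC background. Combined rSBA results, where sampling is also unequal, have no matching provision.

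At stake is how the rSBA description is read. hSBA is run on every sample and rSBA on the quota sample, so an hSBA and an rSBA figure under the same group or vaccine label could describe different mixes of children.

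**Working it through.** **Plan's own figures.** At the 25% MenC-CRM floor, 0.25 × 204 = 51 and 0.75 × 204 = 153 (Table 5.1 prints 52 and 152); 0.25 × 102 = 25.5 and 0.75 × 102 = 76.5 (printed 26 and 76). These agree within rounding. The groups sum to 306 + 306 + 204 + 102 = 918, and the rSBA subset to 100 + 100 + 100 + 50 = 350.

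**Sampling fractions (quota / planned stratum size).**

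| Stratum | At CRM floor | At 50% cap |
|---|---|---|
| Naive | 100/306 = 32.7% | 32.7% |
| MenC-TT, Group 3 | 50/152 = 32.9% | 50/102 = 49.0% |
| MenC-CRM, Group 3 | 50/52 = 96.2% | 50/102 = 49.0% |

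Group 4 gives the same fractions (25/76, 25/26, 25/51).

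**Mix in the subset against the mix in the trial.**

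| Summary | Subset | Trial | Gap (points) |
|---|---|---|---|
| Groups 3, 4: CRM share, floor | 50% | 52/204 = 25.5% | 24.5 |
| Groups 3, 4: CRM share, cap | 50% | 50% | 0 |
| MenACYW (Groups 1+3): primed share | 100/200 = 50% | 204/510 = 40% | 10 |
| Nimenrix (Groups 2+4): primed share | 50/150 = 33.3% | 102/408 = 25% | 8.3 |

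The whole-vaccine gaps hold at every permitted CRM share, because primed children are sampled at 49.0% overall (100/204, 50/102) and naive children at 32.7%.

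**Size of the distortion.** For two strata, the distortion is gap × stratum difference, on the percentage or log-titre scale. The documents give no stratum differences, so these are assumed ranges.

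- *GMT, Group 3 or 4 at the floor:* a 2- to 4-fold CRM/TT ratio gives 2^0.245 = 1.19 to 4^0.245 = 1.40. If TT is the higher carrier, the factors are the reciprocals. At the cap the factor is 1.
- *GMT, whole vaccine, taking the two carriers as equal:* a 2-, 4- or 10-fold primed/naive ratio gives 2^0.10, 4^0.10, 10^0.10 = 1.07, 1.15, 1.26 for MenACYW. For Nimenrix, with exponent 0.0833, it gives 1.06, 1.12, 1.21.
- *Day 0 percentage, MenACYW:* with 10% of naive and 50 to 70% of primed children at or above the cut-off, the subset shows 0.5 × 10 + 0.5 × 50 = 30% up to 0.5 × 10 + 0.5 × 70 = 40%. At the trial mix it is 0.6 × 10 + 0.4 × 50 = 26% up to 0.6 × 10 + 0.4 × 70 = 34%.
- *Day 30 percentage, Nimenrix serogroup C at ≥ 1:128:* Protocol 1.2.2.2 reports 81/86 = 94.2% in naive toddlers. With an assumed 100% in primed children, the trial mix gives 0.75 × 94.2 + 0.25 × 100 = 95.6%, and the subset gives 0.667 × 94.2 + 0.333 × 100 = 96.1%.

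**Precision cost of weighting.** With weight w = stratum size / quota, the design effect is n Σ n_h w_h² / (Σ n_h w_h)². At the floor:

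- Group 3: 100 × 50 × (3.04² + 1.04²) / 204² = 1.240; interval wider by √1.240 = 1.114.
- MenACYW, own mix: 200 × (100 × 3.06² + 50 × 3.04² + 50 × 1.04²) / 510² = 1.117; √ = 1.057.
- Nimenrix, own mix: 150 × (100 × 3.06² + 25 × 3.04² + 25 × 1.04²) / 408² = 1.076; √ = 1.037.

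These assume equal stratum variances. If the TT standard deviation were 1.5 times the CRM one (an assumption), the Group 3 ratio would be √[(0.745² × 2.25 + 0.255²)/50] / √[1.625/100] = 1.27.

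**The case against.** The strongest reply is that combined rSBA columns are an inference. The output lists name no table columns, the whole-vaccine objectives name no assay, and the RCDC sentence does not name rSBA. SAP 5.1.3.2 spells out Groups 1 and 3 together, and 2 and 4 together, only for safety tables. This stands in part: the objectives, the endpoint naming both assays and the RCDC sentence together strongly imply pooling, but no text commits to it.

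Next, stratum-level reporting is already an objective, and equal carrier quotas serve it well. That stands. The quotas are not the defect; unweighted pooling over them would be.

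A third reply is that the trial mix is itself a design choice, so weighting to it swaps one arbitrary mix for another. For whole-vaccine columns this has force. Weighting each vaccine to its own arm still leaves 40% against 25% primed. With a 4-fold primed/naive ratio and no vaccine effect, the apparent GMT ratio would be 4^0.15 = 1.23, hardly better than 4^0.167 = 1.26 in the unweighted subset.

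Finally, rSBA is observational, no hypothesis is tested on it, no hSBA-against-rSBA comparison is planned, and the footnotes disclose the subset's composition. All of that limits the consequence. The rSBA assay section (Protocol 9.3.1.2) is redacted and may describe how children are selected, so silence on selection is not counted against the plan.

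**Conclusion.** The point holds for whole-vaccine rSBA summaries at any permitted enrolment, by 10 points of primed share for MenACYW and 8.3 for Nimenrix. For Group 3 and Group 4 summaries it holds whenever MenC-CRM enrolment is below 50%, by up to 24.5 points of CRM share.

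A reader might infer that every Group 3 or Group 4 rSBA summary is off. The documents do not support that, because at the permitted 50% cap the quotas equal the group mix. Nor do they support reading this as a threat to the trial's conclusions: the primary and secondary analyses use hSBA and do not depend on the subset. Summaries within the naive, MenC-TT or MenC-CRM strata do not mix strata and are unaffected.

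The mix figures follow from planned numbers alone. The size and direction of any distortion rest on assumed stratum differences. Day 30 percentages are likely to move little, since in the earlier phase II study of naive toddlers they were 94.2% to 100% at ≥ 1:128. GMTs, RCDCs and Day 0 results could move more. This is worth settling before the rSBA tables are programmed.

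**What to change.** In Protocol 12.1.3 and SAP 5.1.3.2, make naive, MenC-TT-primed and MenC-CRM-primed children, by vaccine, the primary rSBA presentation. Then either omit combined rSBA columns and curves or weight them:

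- **Group 3 and Group 4:** weight each carrier stratum by its share of the group in the per-protocol set, using actual rather than planned counts.
- **Whole vaccine:** apply one common stratum mix to both vaccines, stated in advance, so that the two columns can be compared.
- **Intervals:** for percentages, use a stratified interval that remains valid at 0% or 100%, for example a stratified Wilson-type interval. A plug-in stratified variance is zero when every stratum is at 100%, which the phase II rates make plausible.

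The cost is SAP wording and minor programming, with no extra samples or assays. At the 25% CRM floor and with equal stratum variances, the combined interval widens by about 11% for Group 3. It would widen by about 6% for MenACYW and 4% for Nimenrix if each vaccine were weighted to its own mix. The figure for a common mix depends on the mix chosen. Widening can be greater if stratum variances differ. Omitting the combined columns avoids this cost.
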